As mentioned above, meta-analyses, including a recent Cochrane review, show valproate is potentially effective with a moderate to large effect size. However, the Cochrane review identifies several major limitations: most of the trials are low quality, conducted in very different healthcare settings to the UK, and none has measured quality of life or outcomes beyond 3 months. This means it is not clear if it is effective, or cost-effective in the NHS. There is, thus, clinical equipoise and considerable NHS costs associated with valproate augmentation of antipsychotic treatment in schizophrenia. This indicates the need for a high quality long-term double-blind RCT of valproate in the UK to determine its efficacy and cost-effectiveness.

To address this, our study design is a pragmatic 12-month, parallel group, placebo-controlled double-blind randomized controlled trial of augmenting existing AP treatment with valproate in patients (men and women, above 18 years of age) who fulfil DSM-5 criteria for schizophrenia or schizoaffective disorder and have persistent psychotic symptoms despite adequate (non-clozapine) AP treatment. Patients will be randomised 1:1 to either placebo + continuing antipsychotic treatment arm or valproate + continuing antipsychotic treatment arm. Randomisation will be stratified by diagnosis, sex and site. Valproate will be started at 500mg/day and titrated up to a dose of approximately 15 to 30 mg/kg/day of valproate over two weeks, in line with evidence that this dose range may be effective [18]. The placebo group will receive a matching placebo titration. To ensure treatment is optimised for each patient, and to promote retention in the trial, further dose increments or decrements will be allowed in both arms providing the dose does not exceed 2500mg/day.

The primary outcome is psychotic symptom severity after 12 months, measured using the PANSS positive subscale. Our secondary outcome measures include discontinuation rates, changes in clinical global impression scale (CGI-SCH), the development of adverse effects, cost-effectiveness and quality of life. Cost-effectiveness will be assessed using the Client Service Receipt Inventory; symptom severity will be assessed using the PANSS positive subscale; and quality of life will be assessed using the quality-adjusted life years (QALYS).

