Valproate will be started at 500mg/day and titrated up to a dose of approximately 15 – 30 mg/kg/day (in steps of 500 mg/day), in line with evidence that this dose range is effective and corresponds to the dose range used in clinical practice [18, 23]. The initial titration will occur over approximately two weeks (Refer to Appendix 1). The placebo group will receive a matching placebo titration. To ensure that the treatment is optimised for each patient, and to promote retention in the trial, further dose increments and decrements of valproate will be allowed in both arms at the treating clinician's discretion up to a maximum of 2500mg/day. The side effects will be evaluated by the UKU Side Effect Rating Scale while deciding dose titration or modification.

The primary outcome measure will be change in the PANSS positive subscale at 12 months. Secondary measures as well as pharmacoeconomic measures will be collected at various time-points described later in the trial flow chart section. The study will be conducted over a period of approximately 5 years. If patients consent, then we will also involve their caregivers as part of the study. They will be provided with information about the study and we will involve them in improving study compliance and some of them will be part of the service user and career group that will be set up at each site to advise us on implementation and feedback.

The trial management group (TMG) chaired by the PI will include the co-PIs and KCL clinical trial unit (KCTU) and the King's Health Partners-clinical trials office (KHP-CTO) representatives. Consultants, study staff members and other collaborators will be included as required. The TMG will meet on a bimonthly basis and report to the trial steering committee (TSC). A training and reliability programme under the stewardship of [name] will be instituted so that research staff will be consistent in their approach across various sites.

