At Visit 2 (Day 1), subjects who continue to meet the study inclusion criteria and none of the exclusion criteria will be randomized to either the placebo or valproate arm. All assessments at baseline (Visit V2) will be done prior to dosing. The study drug will be titrated starting with a dose of 500mg/day to reach a dose between approximately 15mg/kg/day to 30mg/kg/day but not exceeding a total dose of 2500mg per day. Subjects will be asked to take study drug in increments of 500mg (with a minimum interval of 3 days) as illustrated in Appendix 1 over approximately 2 weeks according to their body weight. The placebo arm will also follow the same pattern. An oral gastroresistant tablet of valproate will be used for the study and the dose may be divided twice daily where multiple tablets are taken. A pragmatic dose escalation or reduction of valproate (in steps of 500mg/day) is permitted in this period based on tolerance to the study medication guided by the UKU side effect scale. Halfway through the titration period (1 week +/- 3 days), the study team will contact the subject to review the titration of the study medication and monitor for any side or adverse effects via a faceto-face (especially in case of in-patients) or telephonic conversation. At the end of two weeks (Visit V3), subjects will continue to receive the dose that they can tolerate for the remainder (50 weeks) of the study. The dose of valproate can be varied in the remainder period, if needed, at the investigator's discretion. If the dose is either increased or decreased after V3, a face-to-face or telephonic conversation will be conducted with the subject between 3 to 7 days after the change of dose to check they have completed the dose titration and assess tolerability.

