5.2 Dosing Regimen

The two treatment arms for the trial will be sodium valproate or placebo. The IMP will be started at a dose of 500mg/day and gradually increased to a dose not exceeding 2500 mg/day over two weeks in steps of 500mg depending on body weight over a two week period (Refer to Appendix 1- Dose titration). The placebo group will receive a matching placebo titration. To ensure treatment is optimised for each patient, and to promote retention in the trial, further dose increments/decrements will be allowed in both arms at the treating clinician's discretion depending on side-effects and response and up to a maximum of 30mg/kg/day such that the dose does not exceed 2500mg/day. At the end of the 52-week treatment period, the dose of valproate will be down titrated in steps of 500mg in 3-4-day intervals by patients. The down-titration will also be done when patients exit the trial early. There are no special dietary or life-style requirements that are needed to be adhered to, but patients will be advised that alcohol intake is not recommended during treatment with valproate.

Withdrawal effects have not been reported. Nevertheless, at the end of the study or in the event of a patient wishing to discontinue valproate, the drug will be down titrated over at least two weeks to reduce the risk of a relapse.

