5.5 Storage of IMP

Sodium Valproate is hygroscopic. Container packs must be stored in a dry place below 25°C. The tablets should not be removed from their pack until immediately before they are taken. Instructions to close the container immediately after each use will be conveyed to patients and displayed on labels.

The investigator or designee is responsible for storing the drug in a secure location, which should always be maintained under the strict control of qualified staff.

5.6 Subject Compliance.

Adherence to the antipsychotic medication will be monitored using the medication adherence rating scale [43]. The patient will be asked to respond to the statements in

the questionnaire by circling the answer which best describes their behaviour or attitude towards their medication during the past week. A rating of at least >4 to their antipsychotic medication will be necessary for the participant to participate in the trial. If compliance to their antipsychotic and/or study medication drops below 4 on the medication adherence rating scale the subject will be counselled, and steps taken to improve compliance will be taken up (e.g. offering reminders or seeking carer's help).

Patients will receive dosing instructions about valproate in a patient diary and be instructed to bring all tablet bottles (opened and unopened) to each study visit for assessment of compliance (based on the tablets remaining in the bottles).

Compliance will be documented on the source record by the research assistant. If compliance is $\leq 80\%$ of the correct dosage as prescribed, the investigator or designee must counsel the patient and ensure steps are taken to improve compliance.

If a patient appears to be taking more tablets than prescribed and the dose taken is greater than 30mg/kg/day or 2500mg/day it will be reported to the trial steering committee.

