Appendix 1 Dose titration chart for 500mg sodium valproate tablets

Body Weight Range (kg)	Days 1 -3	Days 4 – 6	Days 7 – 9	Days 10 – 12	Days 13 - 15	Day 16 onwards	Maximum number of tablets that can be taken so it does not exceed 30mg/kg/day or 2500mg/day
35-49	1	1	2	2	2	2	2
50-69	1	1	2	2	3	3	3
70-84	1	1	2	2	3	3	4
85-99	1	1	2	2	3	3	5
100-134	1	2	3	3	4	4	5
>134	1	2	3	4	4	5	5

The titration is a guideline so that all weight categories exceed 15mg/kg/day. Doses will be guided by individual patient's ability to tolerate the medication. Changes to doses (increase or decrease) in individual patients can be made after the titration phase as long as it does not exceed the 30mg/kg/day or 2500mg/day threshold

After V3 (visit 3 - end of titration phase) any changes in dose will be followed by a telephonic assessment (face-to-face especially for in-patients) after 3 to 7 days on the new dose of medication to assess tolerability and suitability to continue that dose.

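### Section 4.2 and the Background cap later dose increases at 2500 mg/day and omit the 30 mg/kg/day limit of Section 5.2 and Appendix 1, so below 83.3 kg the protocol states two maximum doses

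*Protocol*

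**What the plan says.** Five places in the protocol deal with how far the dose may go after the two-week titration, or with what counts as too much.

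- **Background & Rationale:** "further dose increments or decrements will be allowed in both arms providing the dose does not exceed 2500mg/day".
- **Section 4.2:** later increments and decrements are "allowed in both arms at the treating clinician's discretion up to a maximum of 2500mg/day".
- **Section 4.3, Treatment period:** "The dose of valproate can be varied in the remainder period, if needed, at the investigator's discretion". No ceiling is restated there.
- **Section 5.2:** later changes are allowed "up to a maximum of 30mg/kg/day such that the dose does not exceed 2500mg/day".
- **Appendix 1:** changes after titration are allowed "as long as it does not exceed the 30mg/kg/day or 2500mg/day threshold". The chart also gives a maximum number of 500 mg tablets for each weight band.

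Section 5.6 uses both limits for reporting to the steering committee: the patient must appear to take more tablets than prescribed, and "the dose taken is greater than 30mg/kg/day or 2500mg/day".

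Sections 4.2 and 4.3 do mention body weight, but for the initial titration. In Section 4.2 the dose is "titrated up to a dose of approximately 15 – 30 mg/kg/day (in steps of 500 mg/day"; in Section 4.3 it is titrated "to reach a dose between approximately 15mg/kg/day to 30mg/kg/day but not exceeding a total dose of 2500mg per day".

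**The concern.** The same act, raising the dose after titration, has one ceiling in two places and two ceilings in two others. The sentences in Sections 4.2 and 5.2 are nearly the same apart from the missing weight limit, which suggests that a condition was dropped, not that a different rule was meant. Nothing in the protocol says which section prevails.

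A lighter patient could therefore be prescribed a dose that complies with Section 4.2 and breaches Section 5.2. Upward adjustment is foreseeable: Section 5.2 lets the dose follow response as well as side effects, and Section 6.1 admits only patients with at least one positive symptom of moderate severity or more.

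The safeguards would catch such an excess only in part:

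- The Section 5.6 report needs intake above the prescription, so a prescribed excess does not trigger it.
- Drug levels are analysed after the trial (Section 9.1), so they cannot reveal it in time.
- Liver function and blood counts on treatment are scheduled only at 3 and 12 months or at early exit (Sections 4.3 and 5.3), with earlier liver tests prompted by symptoms.

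**Working it through.** **Inputs.** Tablet strength 500 mg (Section 5.1). Flat ceiling 2500 mg/day, or 5 tablets (all sections that state a cap). Weight limit 30 mg/kg/day (Section 5.2, Appendix 1). Appendix 1 maxima of 2, 3, 4, 5, 5 and 5 tablets for 35-49, 50-69, 70-84, 85-99, 100-134 and over 134 kg.

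**Step 1: reproduce the chart.** Under the joint cap, maximum tablets = min(5, whole part of 30 × weight / 500), taken at the lowest weight of each band:

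- 35 kg: 2.1, so 2
- 50 kg: 3.0, so 3
- 70 kg: 4.2, so 4
- 85 kg: 5.1, so 5
- 100 kg: 6.0, limited to 5
- 135 kg: 8.1, limited to 5

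This matches Appendix 1 in every band, so the chart was built on both limits together.

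**Step 2: where the ceilings part.** The weight limit is the stricter one when 30 × weight < 2500, that is, below 2500/30 = 83.3 kg.

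**Step 3: size of the gap.** Dose per kg at the flat ceiling is 2500/weight.

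| Weight band (kg) | Appendix 1 maximum (mg/day) | mg/kg at that maximum, lowest weight | mg/kg at 2500 mg/day, lightest to heaviest | 2500 ÷ chart maximum | Tablets above chart |
|---|---|---|---|---|---|
| 35-49 | 1000 | 1000/35 = 28.6 | 71.4 to 51.0 | 2.5 | 3 |
| 50-69 | 1500 | 1500/50 = 30.0 | 50.0 to 36.2 | 1.67 | 2 |
| 70-84 | 2000 | 2000/70 = 28.6 | 35.7 to 29.8 | 1.25 | 1 |
| 85-99 | 2500 | 2500/85 = 29.4 | 29.4 to 25.3 | 1.0 | 0 |
| 100-134 | 2500 | 2500/100 = 25.0 | 25.0 to 18.7 | 1.0 | 0 |
| Over 134 | 2500 | below 18.7 | below 18.7 | 1.0 | 0 |

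As an example, 2500 mg/day at 60 kg is 41.7 mg/kg. Section 4.2 allows it; Section 5.2 stops at 30 × 60 = 1800 mg, and the chart at 1500 mg.

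**Step 4: the edge of the 70-84 kg band.** Between 83.3 and 84 kg, 2500 mg is within 30 mg/kg (2500/84 = 29.8) but one tablet above the chart. There the flat ceiling conflicts only with the chart.

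**Step 5: does Section 4.2 supply the weight limit elsewhere?** Its 15-30 mg/kg/day range is described as approximate and states where the titration ends. Its pointer to Appendix 1 sits in the sentence on the initial titration. The next rule, on further changes, names a maximum of its own. So the weight limit does not carry over on a plain reading.

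**The case against.** The strongest reply is that this is an omission in summary text. The 2500 mg/day ceiling is correct everywhere; Section 5.2 and Appendix 1 only add a stricter condition, and a prescriber who meets both limits complies with every section. Background & Rationale and the design overview are not where dosing is set. Section 5.2 and the chart are, and they are complete and agree with each other and with Section 5.6. The synopsis gives the dose range as dependent on body weight, and anyone who follows Section 4.2 to Appendix 1 finds the post-titration maximum on the same page. Section 4.3 is merely silent on the cap. The 71.4 mg/kg figure needs a 35 kg adult taken three tablets past the printed maximum, despite contact 3 to 7 days after each change and a dose review at any UKU item rated 2.

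Most of this stands and limits the weight of the point. The operative text is right, the worst case is remote, and the safeguards are real, although they check tolerability and not whether the dose is within 30 mg/kg. What does not stand is the claim that there is no conflict. Section 4.2 names its own maximum for later increases, that maximum is too high for patients below 83.3 kg, and no rule of precedence tells a site or monitor which sentence to apply.

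**Conclusion.** The concern holds. For patients below 83.3 kg the protocol states two different maximum doses of the study drug, and the one in Background & Rationale and Section 4.2 exceeds the protocol's own weight-based limit. The excess over the chart can reach 3, 2 or 1 tablets in the three lowest weight bands; from 85 kg there is none.

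The figures are upper bounds. They assume a prescriber who applies Section 4.2 without consulting Section 5.2 or the chart. How many patients would be exposed cannot be estimated, because the protocol gives no weight distribution. Severity is moderate: it should be fixed because it is a stated dose limit that bears on safety, but the correct limit already stands in the dosing section and the chart. Type I error, power and the planned analyses are unaffected.

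**What to change.** In Background & Rationale and in Section 4.2, end the sentence on further dose changes with: *up to the maximum number of tablets for the patient's weight in Appendix 1 (not above 30 mg/kg/day or 2500 mg/day, whichever is lower)*. For consistency, add the same words in Section 4.3 where the dose may be varied after Visit 3.

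The Appendix 1 maximum is a safe single reference, because its highest dose in any band is 30.0 mg/kg (3 tablets at 50 kg). It also settles the 83.3-84 kg case in favour of the chart.

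The cost is one phrase in three places and a short memo to sites. No new data, patients or analyses are needed. Extending the Section 5.6 report to prescribed excesses would be a further option, but it is not needed to remove the contradiction.

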4.3 Trial Flowchart

The study will consist of three periods. Screening, a treatment period and a long-term follow-up period. The schematic of the first two periods are shown in Figure 1. The Trial Schedule (Table 1) at the end of this section gives a snap shot of all clinical assessments that will be performed.

Figure 1: Study Schematic

Study visit V3, can take place + / - 3 days from the specified week while study visits V4, V5 and V6 can take place within +/- 2 weeks of the specified week. The same apply to the respective dispensing visits. At the end of the 12-month period, down-titration will take place over approximately two weeks depending on the maintenance dose in steps of 500mg in 3-4 day intervals. V7 is the follow up visit after valproate/placebo has been completely stopped and can take place within one week after the last consumed study drug. Assessments will be conducted as closely as possible to the timeframe mentioned however if a major variation arises, it will be factored in the analysis. A single follow up via telephone or face-to-face, 60 days since their last study drug intake will also be conducted to record for any AEs/SAEs

Screening period (approximately – 8 to 0 weeks)

Clinical teams will first alert suitable patients to the study. If the patients are interested in being contacted by the research team, then the research team will get in touch with them. If patients have already given consent to be contacted for research (for example through a consent-to-consent procedure), then the study team will make contact directly and if the patient consents then the patient's clinical care provider will be informed of their participation. Patients will also be allowed to contact the study team via adverts displayed in waiting rooms, and relevant media (e.g. patient newsletters). When contacted or if the study team has permission to contact the patient then a member from the study team will have a face to face conversation or via the telephone to give the patient more details about the study. If the patient is interested in participating in the study, they will then be invited for consenting and screening where

further details of the study will be discussed and the informed consent form (ICF) of the study will be presented.

Informed consent will be obtained from each subject before any study procedures are performed. Demographics (date of birth, sex, ethnicity, race), prior and current medications, and medical and psychiatric history will be collected. If the subject's historical medical care was provided at another institution or location, the subject's consent will be sought to obtain these outside records where necessary to verify that the subject meets all inclusion and none of the exclusion criteria.

A primary psychiatric diagnosis of schizophrenia or schizoaffective according to DSM-5 must be met. A structured clinical interview for DSM-5 (SCID-5) will be used for the purpose of making a diagnosis. Clinicians administering the SCID should be familiar with the DSM-5 classification and diagnostic criteria and should have the appropriate training. It takes approximately 30 minutes to complete it. The severity of psychopathology will be measured using the Positive and Negative Syndrome Scale (PANSS). A total PANSS score of greater than 70 plus one or more psychotic item rating of moderate or greater severity must be met. Clinicians administering PANSS should be familiar with the scale and it takes 30 minutes to administer it. Subjects must be on at least one antipsychotic at a dose above the minimum therapeutic dose in the approved dose range in the label for a minimum of 6 weeks at the time of screening. Any change to dose must occur 2 weeks prior to screening. The dose and formulation of the antipsychotic can change during the trial. Also switching to a non-clozapine antipsychotic will be allowed. If more than one non-clozapine antipsychotic is needed, then it will be permitted. However, switching to clozapine will result in the patient being discontinued from the study medication.

Subjects should also meet other inclusion and none of the exclusion criteria necessary for the study and, if needed, a blood screen for liver function and full blood cell count will be carried out. Pregnant or breast-feeding women, women of child-bearing potential who do not agree to the contraceptive methods needed for participating in the trial will be excluded. Women of child-bearing potential must meet the MHRA pregnancy prevention programme and agree to an annual risk acknowledgement plan for pregnancy prevention. A pregnancy test must be negative for all women of childbearing potential to participate in the trial. Also, patients who pose immediate or significant risk for suicide will be excluded.

The screening must occur prior to randomization to the study and the study medication will not start within 24 hours of written consent. If the screening could not be completed within 8 weeks from the day of the signed consent, then inclusion criteria will be reassessed by the investigator and clinical tests will be redone if judged necessary by the research team. The eight-week period will then again apply for the reassessment and it will be the final attempt to include the subject under the consent that was obtained. Assessments at the screening stage are described in the Trial Schedule (Table 1).

Treatment period (Week 0 - 52 followed by discontinuation period)

At Visit 2 (Day 1), subjects who continue to meet the study inclusion criteria and none of the exclusion criteria will be randomized to either the placebo or valproate arm. All assessments at baseline (Visit V2) will be done prior to dosing. The study drug will be titrated starting with a dose of 500mg/day to reach a dose between approximately 15mg/kg/day to 30mg/kg/day but not exceeding a total dose of 2500mg per day. Subjects will be asked to take study drug in increments of 500mg (with a minimum interval of 3 days) as illustrated in Appendix 1 over approximately 2 weeks according to their body weight. The placebo arm will also follow the same pattern. An oral gastroresistant tablet of valproate will be used for the study and the dose may be divided twice daily where multiple tablets are taken. A pragmatic dose escalation or reduction of valproate (in steps of 500mg/day) is permitted in this period based on tolerance to the study medication guided by the UKU side effect scale. Halfway through the titration period (1 week +/- 3 days), the study team will contact the subject to review the titration of the study medication and monitor for any side or adverse effects via a faceto-face (especially in case of in-patients) or telephonic conversation. At the end of two weeks (Visit V3), subjects will continue to receive the dose that they can tolerate for the remainder (50 weeks) of the study. The dose of valproate can be varied in the remainder period, if needed, at the investigator's discretion. If the dose is either increased or decreased after V3, a face-to-face or telephonic conversation will be conducted with the subject between 3 to 7 days after the change of dose to check they have completed the dose titration and assess tolerability.

Clinical assessments will be performed as described in the Trial Schedule (Table 1). Blood samples for determination of liver functioning and full blood counts will be assessed at the 3-month time point (Visit 4) and at the 12-month time point (Visit 6). If a subject were to exit early, then these tests will be conducted at exit. Blood samples for post-hoc analysis of epigenetic changes and drug levels will be collected at V2 prior to the start of medication and then at the end at V6. The rationale for this is that valproate may cause epigenetic changes [40] and we will measure these changes in DNA collected from peripheral blood cells in co-relation to the subject's exposure to valproate and determine if this is linked to clinical response. These samples may not be collected if a site does not have facilities to take or store them.

At the end of the study (Visit 6, 52 weeks), the study medication will be reduced in steps of 500mg, each step over 3-4 days, lasting up to two weeks depending on the maintenance dose of the subject. The study team will organize a follow up visit (V7, 54 weeks) after the trial drug is completely stopped. Results of blood tests (LFT and TBC) done at V6 will also be conveyed to participants and their clinical care team.

In case of early discontinuation from the study medication, the same dose reduction strategy will be followed (unless a more rapid reduction is required for clinical reasons). An exit interview will be conducted (including cases who complete the 12-month

treatment) to assess blinding, experience of participation, and reasons for early termination if applicable. Clinical assessments as described in the Trial Schedule will also be performed (Table 1).

Long-term follow up (approximately annually after 54 weeks till the end of trial)

Patients will be followed up to determine long-term outcomes annually during the course of the study. Consent for this will be sought at the beginning. The main aim is to assess the long-term clinical outcome afforded by the exposure to valproate and the rate of switch to clozapine between the two arms in the follow-up period. We will extract data that are routinely collected by the clinical teams and recorded in clinical notes electronically. The main outcome will be the HoNOS rating. We will also collect data on other important clinical outcomes including the number of hospitalisations, home treatment episodes, and whether they have started valproate or clozapine.

End of trial

Visit 7 of the last patient recruited for the study (including the 60 day follow-up period to assess AE/SAEs after the last day of medication) will end the trial and hence the long-term follow up will be done up to this period for the entire trial. Hence patients who entered the trial earlier will have longer follow up data compared to ones that enter later.

Table 1: Trial Schedule

Study Visit	V1	V2	V3	V4	V5		V6	V7 [%]	Post 1- year %	Early exit
Study week/month/year	Screening	Baseline ^{\$}	2-week	3-month	6-month	9-month	12-month	Follow up	Annually	
Drug Dispensing session		DS1	DS2	DS3	DS4	DS5	DS6	_		
Obtain informed consent	х									
Review inclusion/exclusion criteria	х	x ¹								
Demography	х									
Prior/concomitant medication review	х	x ¹	x ⁴			х				
Medical history	х		x ⁴			х				
Medication adherence rating scale (for antipsychotic medication)	х	х	Х	х	Х	х	х	х		х
Serum Pregnancy test (women)	х				x ²					
Signed, valid pregnancy risk acknowledgement form as part of the MHRA pregnancy prevention programme		x ²			x²					
Psychiatric history	х						х		х	х
HoNOS	x ^{&}						х		х*	х
Frailty assessment	х									
SCID-5(Research)	х									
Vital signs	х	x ¹	х	х	Х		Х	х		х
Height, Weight &BMI	х	x ¹		Х	Х		Х			х
Liver function test	x [£]			Х			Х			х
Full blood cell count	x [£]			х			х			х
Blood samples (for epigenetic and other analysis)	х	x ⁵		Х			х			х

...continued

Study Visit	V1	V2	V3	V4	V5		V6	V7%	Post 1-year [%]	Early exit
Study week/month/year	Screening	Baseline ^{\$}	2-week	3-month	6-month	9-month	12-month	Follow up	Annually	
Dispensing session		DS1	DS2	DS3	DS4	DS5	DS6			
Urine pregnancy test	x³	x ³	x³	x³	x ³	x³	x ³	x ³		
Dispense IMP		Х	х	х	х	х	x**			
IMP accountability (pill			х	х	х	х	х	х		
count)										
PANSS	х	X ¹		х	х		х	х		Х
CGI		Х		х	х		х			Х
YMRS		Х		х	х		х			Х
C-SSRS		Х		х	х		х			Х
MOAS		х		х	х		х			Х
SWEMWBS		х		х	х		х			Х
SF-36		х		х	х		х			Х
CSRI		х		х	х		х			Х
UKU#		х		х	х		х	х		Х
Exit interview							х			Х

- 1 repeated at baseline visit to ensure inclusion/exclusion criteria is met or is a required safety requirement. Please note that inclusion/exclusion criteria should be met throughout the treatment period with the exception of PANSS score which can vary in response to treatment.
- 2 the annual pregnancy risk assessment form should be checked for completion at baseline. It is valid for one year from the date of signature by the subject and hence it may need repetition during the course of the clinical trial and hence at V5 make sure it is valid till the end of their medication phase
- 3 Optional at clinician discretion (e.g. if there is a gap or change in contraception)
- 4- Assess changes from baseline that require clinical review (e.g. new onset liver disease, new prescription)
- 5-To collect a sample if not already collected at screening
- &Check if subjects have a HoNOS file, if not create one in co-ordination with their clinical team. * HoNOS will be collected on an annual basis till end of trial
- ** Only if needed to complete the down titration.
- £ To be performed at the discretion of the clinician based on clinical history and medical assessment.
- # Unscheduled UKU should be administered if a subject develops a side-effect requiring treatment.
- \$ All assessments at baseline (V2) must be performed pre-dose. Also, a minimum of 24 hours between signing of ICF and dosing will be given for subjects to reflect on their participation.
- % V7 to be scheduled within 1 week after stopping study medication & includes a single follow up via telephone or face-to-face 60 days since their last study drug intake to record for any AEs/SAEs. Most will be further followed up using electronic notes. The last patient who completes V7 (including the 60 day AE/SAE assessment) will result in the end of the trial.

5 Trial Medication

